15.6.3 Secondary Objective #3: Polyfunctionality and Survival

Objective	To assess the association between fold changes in T cell polyfunctionality from baseline to pheresis 2, and survival after vaccine #4.
Analysis Set	All patients who have a baseline (pre vaccine 1) and polyfunctionality assessed at leukapheresis 2 who receive vaccine # 4. Polyfunctionality is assessed at leukapheresis so that results do not reflect the impact of Td-preconditioning post-vaccine 4 assessment of polyfunctionality. Due to budgetary considerations, only the first 24 patients who reach vaccine 4 will be analyzed.
Outcome	Survival from vaccine 4.
Hypothesis	Greater fold changes in polyfunctionality are associated with longer survival.
Analysis Plan	The mean fold change from baseline to leukapheresis 2 will be summarized for the frequency of pp65 antigen-specific CD8 ⁺ T cells producing three or more cytokines (IFN γ , CCL3, IL-2, TNF α , CD107a). Cox proportional hazards model will assess the association between fold change increase between baseline and the leukapheresis 2 in the frequency of pp65 antigen-specific CD8 ⁺ T cells producing three or more cytokines (IFN γ , CCL3, IL-2, TNF α , CD107a), and survival post-vaccine 4. The hazard ratio associate with a 1-unit fold change in polyfunctionality will be estimated with 95% confidence intervals.
Power Analyses	Cox proportional hazards model will assess the impact of fold change of pp65-specific polyfunctional CD8+ T cells between baseline and leukapheresis 2 on survival after vaccine #4. Data from Pro00000580 ERADICATE [132] shows that the SD for fold change in polyfunctionality among vaccinated patients is 1.589, and that the hazard ratio associated with 1 unit increase in fold change is

	approximately 0.609. Assuming SD=1.589, there would be 80% power to detect a hazard ratio of 0.6 assuming a two-tailed test ($\alpha=0.0167$) within a Cox model after 16 deaths [130, 131]. If we assume that the median OS post-vaccine 4 is 24 months, then 16 deaths should be observed approximately 38 months after the 24 th patient receives vaccine 4.
Additional Analyses	Many of the 24 patients who have assessments at pre-vaccine 1 and leukapheresis 2 will also have an assessment of polyfunctionality at pre-vaccine 6. Among those patients who have all 3 assessments, a paired comparison of the fold change in polyfunctionality at pheresis 2 and vaccine 6 will be conducted using either a paired t-test or a Wilcoxon signed rank test. These analyses will assess whether levels of polyfunctionality are maintained in the absence of DI-TMZ. In addition, the Wilcoxon rank sum test will assess whether significant fold changes occur at pheresis 2.

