15.6 Secondary Objectives

This study has five secondary objectives. The first 3 secondary objectives examine the impact of functional measures of CMV pp65-loaded DC vaccine efficacy on survival post-vaccine. These measures include migration (Section 15.6.1), fold change in CCL3 (Section 15.6.2), and fold change in pp65 antigen-specific polyfunctionality (Section 15.6.3). Power calculations will be provided for each of the secondary objectives. Power calculations for the three functional predictors of survival post-vaccine 4 will be adjusted to account for multiple comparisons using a Bonferroni correction, and will use a type I error rate of 0.0167.

The other secondary objectives include an assessment of whether the percent of T_{Reg} of CD4+ T cells remains stable or decreases without additional temozolomide after vaccine 1 (Section 15.6.4), and an assessment of the safety of the protocol's treatment regimen (Section 15.6.5).

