15.6.2 Secondary Objective #2: CCL3 and Survival

Objective	To assess the association between CCL3 measured post-Td administration and survival after vaccine # 4.
Analysis Set	All patients who undergo assessment of CCL3 after Td administration. All patients who reach vaccine 4 when Td is administered will be included in analyses. Forty (40) patients are anticipated.
Outcome	Survival from vaccine 4.
Hypothesis	Greater levels of CCL3 are associated with longer survival.
Analysis Plan	The Cox proportional hazards model will assess the impact of CCL3 on survival post-vaccine 4. The hazard ratio associate with a 1-unit increase in CCL3 will be estimated with 95% confidence intervals.
Power Analyses	Cox proportional hazards model will assess the impact of CCL3 on survival post-vaccine 4. Within ATTAC [129], the standard deviation for CCL3 was 12.9 and the hazard ratio for survival post-vaccine 4 was approximately 0.95 for a 1 unit increase in CCL3. Assuming SD=12.9, there would be 80% power to detect a hazard ratio of 0.95 with a two-tailed test ($\alpha=0.0167$) within a Cox model under these assumptions after 24 deaths [130, 131]. If we assume that the median OS post-vaccine 4 is 24 months, then 24 deaths should be observed approximately 20 months after the 40 th patient receives vaccine 4.

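### The 80% power stated for the CCL3 and polyfunctionality Cox analyses comes from a large-sample formula that is optimistic at these sizes; simulation gives about 70-75% and 63-73%

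*Combined protocol and SAP*

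**What the plan says.** Section 15.6 sets a Bonferroni level for the three functional predictors of survival after vaccine 4; their power calculations "will use a type I error rate of 0.0167".

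For CCL3, section 15.6.2 takes its inputs from an earlier trial: "the standard deviation for CCL3 was 12.9 and the hazard ratio for survival post-vaccine 4 was approximately 0.95 for a 1 unit increase in CCL3". It then states that "there would be 80% power to detect a hazard ratio of 0.95 with a two-tailed test", "within a Cox model under these assumptions after 24 deaths". On cohort size it says "Forty (40) patients are anticipated".

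For polyfunctionality, section 15.6.3 states that "the SD for fold change in polyfunctionality among vaccinated patients is 1.589". It gives the pilot hazard ratio per unit of fold change in the words "approximately 0.609. Assuming SD=1.589", and then says "there would be 80% power to detect a hazard ratio of 0.6 assuming a two-tailed test", with 16 deaths. For budgetary reasons only the first 24 patients to reach vaccine 4 are analysed.

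Both sections cite a published sample-size method for Cox regression with a non-binary covariate (reference 130) and power software (reference 131). Both assume a 24-month median survival after vaccine 4. Neither says how the covariate is distributed.

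**The concern.** The cited formula treats every death as carrying the same information, proportional to the full variance of the covariate. That is close to true when the effect is small or few of those at risk die. Neither holds here. One SD of CCL3 multiplies the hazard by about 0.52 and one SD of polyfunctionality by about 0.44, while 24 of 40 (60%) and 16 of 24 (67%) of the patients are to have died. High-risk patients tend to die first, so the covariate's spread among those still at risk shrinks and later deaths tell less than the formula credits.

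Section 15.6.1 drops migration, so these are the two biomarker-survival objectives that remain. Section 7.2 makes confirming such biomarkers part of the trial's purpose, and section 15.8 lets available correlative data inform decisions on accrual. The stated power should therefore be what the design delivers.

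**Working it through.** **1. Inputs.** Two-sided alpha 0.0167 (15.6). CCL3: SD 12.9, HR 0.95, 24 deaths, 40 patients (15.6.2). Polyfunctionality: SD 1.589, HR 0.6 (pilot 0.609), 16 deaths, 24 patients (15.6.3). Median survival after vaccine 4: 24 months.

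**2. Reproducing the plan's figures.** With b = SD x |ln HR|, the formula is D = (z(1-alpha/2) + z(0.80))^2 / b^2, and power = Phi(sqrt(D) x b - z(1-alpha/2)). Here z(1-0.00835) = 2.393 and z(0.80) = 0.842; the squared sum is 10.46.

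- CCL3: b = 12.9 x 0.0513 = 0.662, HR per SD = exp(-0.662) = 0.52. D = 10.46 / 0.438 = 23.9. Power at 24 deaths: Phi(3.242 - 2.393) = 80.2%.
- Polyfunctionality at 0.6: b = 1.589 x 0.5108 = 0.812, HR per SD = 0.44. D = 10.46 / 0.659 = 15.9. Power at 16 deaths: Phi(3.247 - 2.393) = 80.3%.

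Both stated figures are reproduced.

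**3. The pilot hazard ratio.** At 0.609, b = 1.589 x 0.4959 = 0.788. D = 10.46 / 0.621 = 16.85, so 17 deaths. Power at 16 deaths: Phi(3.152 - 2.393) = 77.6%. This step needs no simulation and no distributional assumption.

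**4. Simulation at the planned sizes.** Exponential survival with a 24-month median, single-covariate Cox model, data cut at the planned death. The covariate shape is an assumption, so several were tried. Power (%) is shown as score / likelihood-ratio / Wald, with 8,000 replicates per cell (5,000 for the lognormal row).

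| Covariate | CCL3, 24 of 40 | Polyfunctionality, HR 0.6, 16 of 24 | Polyfunctionality, HR 0.609, 16 of 24 |
|---|---|---|---|
| Normal | 71.6 / 72.1 / 70.9 | 66.2 / 67.7 / 63.8 | 63.8 / 65.0 / 61.5 |
| Normal, scaled to the stated SD in each sample | 74.2 / 74.8 / 73.4 | 68.5 / 70.2 / 66.5 | 65.6 / 66.7 / 63.0 |
| Uniform | 73.8 / 73.8 / 71.9 | 70.4 / 70.4 / 66.8 | 68.4 / 68.6 / 64.8 |
| Two-point | 76.3 / 75.7 / 73.0 | 74.9 / 73.9 / 67.5 | 71.2 / 70.2 / 64.1 |
| Lognormal, log-scale SD 0.8 | 25.1 / 46.9 / 23.5 | 20.7 / 40.7 / 17.1 | not run |

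With a normal covariate and staggered entry, Wald / likelihood-ratio power was 71 / 72 for CCL3, 63 / 66 for polyfunctionality at 0.6, and 60 / 64 at 0.609. Mild right skew gave 55-67% for CCL3 and 46-63% for polyfunctionality.

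**5. Is the gap real?** With no effect the rejection rate was 0.019 for CCL3 and 0.018-0.021 for polyfunctionality, close to the nominal 0.0167. With 400 patients and the same numbers of deaths, power returned to 79-80%. The shortfall is therefore a finite-sample effect and not a fault in the code.

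**6. What would give about 80% (normal covariate).** At the planned deaths: HR of about 0.945 per CCL3 unit, or about 0.54 per unit fold change. Alternatively, for CCL3 at HR 0.95, about 30 of 40 deaths (Wald / likelihood-ratio 80 / 81).

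**The case against.** The strongest reply is that the plan names a published method and applies it correctly. Steps 2 and 4 bear this out: the 80% is reproduced exactly, and the lower figures appear only once a covariate distribution is added that the documents do not give. The size of the shortfall depends on that choice. This stands, and it is why the result is given as a range. It does not rescue the 80%, because every shape tried at the planned patients and deaths fell below it.

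The rounding of 0.609 to 0.6 is disclosed and changes the count by one death, which is small against the uncertainty of a pilot estimate. That is fair; it is a minor, separate optimism.

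Three stronger readings are tempting, and the documents do not support them.

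- A reader might infer that the sponsor miscalculated. The formula was applied correctly; it is the approximation that fits poorly.
- A reader might infer that 24 patients can never give 80% power for polyfunctionality. With all 24 dead, score / likelihood-ratio / Wald power was 82 / 82 / 80 for a uniform covariate, 85 / 83 / 80 for a two-point covariate and 81 / 81 / 79 for a normal covariate scaled in each sample. Only the unscaled normal draw stayed below 80% on all three tests (77 / 78 / 76).
- A reader might infer that the plan would treat a non-significant biomarker result as evidence of no association. Sections 15.6.2 and 15.6.3 contain no such rule and report hazard ratios with 95% confidence intervals, which show the imprecision directly. Section 15.6.4 has an inference rule of that kind, but for regulatory T cells.

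**Conclusion.** The concern holds as a matter of optimistic approximation. The stated 80% is what the cited formula returns, but the planned designs do not deliver it in simulation. In round figures, power is about 70-75% for CCL3 and 63-73% for polyfunctionality with symmetric covariates; the most favourable single cells reach 76% and 75%. A normal covariate gives about 70-72% and 63-68% across the three tests. Right skew lowers both, to 55-67% and 46-63% when mild. Skew is plausible for serum concentrations and fold changes, which cannot be negative, but the documents do not say.

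These figures rest on the plan's SDs, hazard ratios, alpha, patients and deaths, on exponential survival, and on an assumed covariate shape. The direction is firm; the exact size is not. The 0.609 against 0.6 point (17 deaths; 77.6% at 16) rests on the plan's own formula alone.

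**What to change.** - In 15.6.2 and 15.6.3, replace the 80% with simulated power, naming the assumed covariate distribution and giving the range: about 70-75% and 63-73% for symmetric covariates, lower if right-skewed. Alternatively, state the hazard ratios that have about 80% power under a normal covariate: about 0.945 per CCL3 unit and about 0.54 per unit fold change.
- In 15.6.3, use 0.609 or justify 0.6.
- Describe the polyfunctionality analysis as limited in power at 16 deaths.
- Optionally, tie the 80% for CCL3 to about 30 deaths (normal covariate). This needs longer follow-up but no more patients, because section 12.6.2 already follows patients who started dose-intensified temozolomide until death or loss to follow-up.

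The cost is SAP wording and a short simulation. The drawback is that the stated power becomes less favourable.

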12.3 End of Treatment

Vaccines are given as described above for a total of 10 or until progression (whichever comes first). Once the vaccinations are complete, the treatment phase of the study will be over and the follow-up period will begin.

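### Section 15.6.3 tests whether T cell polyfunctionality is maintained to vaccine 6 with a paired difference test and no margin or interval, so a non-significant result could not support that conclusion

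*Combined protocol and SAP*

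**What the plan says.** The analysis is described under Additional Analyses in Section 15.6.3 of the combined protocol and SAP. It is limited to complete cases: "Among those patients who have all 3 assessments, a paired comparison of the fold change in polyfunctionality at pheresis 2 and vaccine 6". The test is to be a t-test on the pairs or its signed rank alternative. Its purpose is given in one sentence: "These analyses will assess whether levels of polyfunctionality are maintained in the absence of DI-TMZ".

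The number of pairs is capped, because for budget reasons "only the first 24 patients who reach vaccine 4 will be analyzed". How many of them will contribute is left open: "Many of the 24 patients who have assessments at pre-vaccine 1 and leukapheresis 2 will also have an assessment of polyfunctionality at pre-vaccine 6".

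Three other places bear on the reading:

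- Section 12.3 ties vaccination to progression: "Vaccines are given as described above for a total of 10 or until progression". A pre-vaccine 6 sample therefore comes from a patient still being vaccinated.
- Section 9.1 and Table 4 place intradermal Td and vaccine 4 three (±1) weeks after leukapheresis 2, with later vaccines every 35 (±7) days. The single DI-TMZ cycle comes before vaccine 1.
- Section 15.6.4 (T_Reg) asks a similar question about stability and attaches a number to the answer: a mean change below 0.71 is read as no increase. Section 15.6.3 has no counterpart for polyfunctionality.

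**The concern.** The question is whether a level has been kept, but the tool named is a test for a difference. Such a test can give evidence of a fall. When it is not significant, it cannot tell a stable response from a fall too small for the sample to detect. With no margin, interval rule or power statement, the p-value is the only output the plan names for this comparison, and a report could easily describe a non-significant result as a maintained response.

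Two features limit what even a clear result would mean. The patients compared are those who had not progressed and were still on vaccine, so the result does not describe all 24. The second sample also follows Td pre-conditioning and two further vaccines, so it shows the response under continued treatment.

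At stake is one supporting statement about durability. Table 1 lists mean fold change at vaccine 6 among the secondary endpoints, so it is likely to be reported. No primary claim or go/no-go rule depends on it.

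**Working it through.** **Inputs from the documents**

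- SD of fold change among vaccinated patients: 1.589 (Section 15.6.3). This is a between-patient SD.
- Pairs: at most 24 (Section 15.6.3).
- T_Reg comparison: criterion 0.71, SD 1.65, n = 48, one-tailed 0.05 (Section 15.6.4).

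**Assumptions, because the documents do not give them**

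- Within-patient correlation ρ between the two fold changes: 0.3 to 0.7.
- Pairs available: 24 (the best case) and 18 (illustrative only).
- Two-sided α = 0.05. The section states no α for this test.
- True mean loss: 0.5 or 1.0 fold-change units. The plan does not say what loss matters.

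**Step 1: the plan's own figures.** Section 15.6.3 sizes only its Cox analysis. With D = (z₁₋α/₂ + z₀.₈₀)² / (SD² × (ln HR)²), α = 0.0167 and HR 0.6:

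D = (2.393 + 0.842)² / (1.589² × 0.2609) = 10.464 / (2.525 × 0.2609) = 15.9, so 16 deaths, as stated.

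The T_Reg figure also reproduces: a one-sided t-test with n = 48, SD 1.65 and a true mean of 0.71 has 90.2% power against the stated 90%. No figure is given for the leukapheresis 2 versus vaccine 6 comparison.

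**Step 2: SD of the paired difference.** SD_d = 1.589 × √(2(1 − ρ)).

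- ρ = 0.3: 1.589 × √1.4 = 1.880
- ρ = 0.5: 1.589 × √1.0 = 1.589
- ρ = 0.7: 1.589 × √0.6 = 1.231

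The between-patient SD equals the paired SD only at ρ = 0.5.

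**Step 3: chance that a true loss is missed.** Power of the paired t-test is P(|T| > t₀.₉₇₅,ₙ₋₁), where T is noncentral t with n − 1 degrees of freedom and noncentrality loss / (SD_d/√n). For example, with n = 24, ρ = 0.5 and loss 0.5, the noncentrality is 0.5 / (1.589/√24) = 0.5/0.324 = 1.54. Power is 31.5%, so the loss is missed 68.5% of the time.

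| Pairs | ρ | Loss 0.5 missed | Loss 1.0 missed | 95% CI half-width |
|---|---|---|---|---|
| 24 | 0.3 | 76% | 30% | 0.79 |
| 24 | 0.5 | 69% | 16% | 0.67 |
| 24 | 0.7 | 52% | 3% | 0.52 |
| 18 | 0.3 | 81% | 43% | 0.93 |
| 18 | 0.5 | 76% | 29% | 0.79 |
| 18 | 0.7 | 63% | 10% | 0.61 |

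The half-width is t₀.₉₇₅,ₙ₋₁ × SD_d/√n, for example 2.069 × 0.324 = 0.67. In every row it exceeds 0.5, so an observed change of zero would still leave a loss of 0.5 inside the interval.

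**Step 4: what lies between the samples.** Leukapheresis 2 to vaccine 6 is 21 + 35 + 35 = 91 days on the nominal schedule (14 + 28 + 28 = 70 to 28 + 42 + 42 = 112). Td, vaccine 4 and vaccine 5 fall in that interval. Both samples come after the only DI-TMZ cycle.

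**The case against.** The strongest reply is that this is one additional analysis and that its wording is open. The plan says the comparison will assess maintenance. It does not say that a non-significant p-value will be reported as maintenance. Table 1 also lists the mean fold change at both time points, so a large fall would be visible whatever the test showed. That is fair as to weight. It does not supply a criterion, and two separate means do not give the precision of the paired change.

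A reader might infer that Td and vaccines 4 and 5 invalidate the comparison, because the same section explains its choice of time point this way: "Polyfunctionality is assessed at leukapheresis so that results do not reflect the impact of Td-preconditioning". The documents do not support going that far. That reason concerns the predictor in the survival model. The phrase about absence of DI-TMZ can fairly mean the protocol regimen with no further cycles, in which case Td and the later vaccines are part of the condition studied. What stands is that the conclusion should say so.

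A reader might also infer that almost any real loss would go unnoticed. The table does not bear this out: with 24 pairs and ρ = 0.5, a loss of 1.0 unit is missed only 16% of the time.

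Finally, a loss could be converted into a hazard using the plan's hazard ratio of 0.609 per unit. That figure describes differences between patients in an earlier study. Nothing in the documents supports applying it to a later fall within a patient.

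**Conclusion.** The concern holds in a limited form. That a non-significant difference test cannot establish maintenance needs no assumption, and Section 15.6.3 offers no other basis for the conclusion. The restriction to patients still on vaccine, and the presence of Td and two vaccines between the samples, follow directly from the schedule and Section 12.3.

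The size rests on the assumed correlation, number of pairs and α set out above. On those, a loss of 0.5 units is more likely to be missed than detected, even with all 24 pairs (52-76%; 63-81% with 18). A loss of 1.0 unit would usually be detected (missed 3-30% with 24 pairs, 10-43% with 18). The exact rate cannot be fixed from the documents.

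A reader might take this for a flaw in a central design question, since the trial gives no adjuvant temozolomide beyond one cycle. The documents do not give it that place. The objective and sizing of Section 15.6.3 concern association with survival, and the Table 1 objective framed around absence of adjuvant temozolomide is the T_Reg one. This is a worthwhile, low-cost correction to a supporting analysis.

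**What to change.** In Section 15.6.3, Additional Analyses:

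1. Report the paired change (or ratio) in fold change from leukapheresis 2 to vaccine 6 with its 95% confidence interval, and base any statement about maintenance on that interval. State that a non-significant p-value will not be read as maintenance.
2. Tabulate the leukapheresis 2 fold change for patients with and without a vaccine 6 sample, with the number in each group, so that selection is visible.
3. Word the conclusion as the level under continued vaccination and Td pre-conditioning without further temozolomide, among patients still on vaccine.
4. Optionally, add a mixed model using all 24 patients as a sensitivity analysis. State its missing-at-random assumption, and note that a modelled vaccine 6 value is hypothetical for a patient who progressed and stopped vaccination. For that reason it should not replace the paired estimate.
5. Reconcile Section 12.7.5, which names only pre-vaccine 1 and leukapheresis 2 as time points for the polyfunctional fold change, with the use of vaccine 6 here.

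The cost is SAP wording and a small amount of analysis, with no new samples or assays. The downside is a narrower claim, and with at most 24 pairs the interval may leave the question of a moderate loss open.

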12.7.5 Immunologic Assessments

Immunological response evaluations will be conducted as described in [Table 4](#). All patients will undergo at least 2 leukapheresis procedures – prior to radiation (1 red top 10mL tube) and approximately 2 weeks post vaccine #3 (9 yellow ACD 8.5mL tubes, 2 red top 10mL tubes). If an additional leukapheresis must occur earlier than 14 (\pm 4) days after vaccine 3, then no immune monitoring will be drawn at this additional leukapheresis. For subjects who complete all 10 study vaccines without progressing, an attempt will be made to obtain blood for immunologic monitoring 2-3 times a year at standard Duke neuro-oncology visits and at progression (whichever comes first). The immune monitoring blood that is collected prior to the initiation of post RT-TMZ cycle 1 (on the same day) will be the baseline for T_{reg} analysis. The immune monitoring blood drawn at pre-vaccine #1 will be the baseline for polyfunctional T cell analysis. The blood drawn on the same day as (but prior to) Td preconditioning will be analyzed for the baseline CCL3. A comparison of pre-therapy lymphocyte functions to those at intervals after each immunization will be made. These tests may provide evidence for the development of immune responses following DCs immunization and will play an important role in the design of future DC-based clinical trials. Cellular immune responses to pp65 will be measured by polyfunctional T cell assays using 10-12 color panels previously optimized in our laboratory, which includes detection of CCL3 on T cells. The effect of treatment on cytokines and other soluble factors will be assayed in the serum/plasma. Serum/plasma will be measured to determine levels of CCL3 from the blood drawn at the Td preconditioning visit, and at the vaccine #4 visit. T_{Reg} kinetics will be measured by using a constellation of markers specific for T_{Reg} s such as foxp3, CD25 and CD4. Whenever blood for immune monitoring is obtained, we will submit a CBC with auto differential to assess absolute number of T_{Reg} s. These will be drawn with SOC blood draws whenever possible.

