15.6.1 Secondary Objective #1: Migration and Survival

PLEASE NOTE: The study originally planned to address secondary objective #1 as described below. However, with the activation of Protocol v.20220204, the plans for examining the relationship between migration and survival have been dropped.

Objective	To assess the association between migration of CMV pp65 RNA-pulsed DCs with GM-CSF to site-draining inguinal lymph nodes after Td pre-conditioning and survival after vaccine # 4.
Analysis Set	All patients who undergo migration studies at vaccine 4. Due to budgetary considerations, only the first 16 patients who reach vaccine 4 will undergo migration studies.
Outcome	Survival from vaccine 4.
Hypothesis	Patients with greater migration will have longer survival.
Analysis Plan	The Cox proportional hazards model will assess the impact of migration on survival after vaccine #4. Migration is defined as the maximum percentage of ¹¹¹ In-labeled DCs reaching inguinal nodes during the 48 hours after the 4 th vaccination. The hazard ratio associated with a 1-unit change in migration will be estimated with 95% confidence intervals.
Power Calculations	Cox proportional hazards model will assess the impact of peak migration at 24 or 48 hours after vaccine 4 on subsequent survival, defined as the time between vaccine 4 and death, or last follow-up if the patient remains alive at the time of analysis. Data from ATTAC [129] show that the standard deviation (SD) for peak migration is 7.86 and that the hazard ratio associated with 1 unit increase in migration is approximately 0.86. Assuming SD=7.86, there would be 80% power to detect a hazard ratio of 0.86 assuming a two-tailed test ($\alpha=0.0167$) within a Cox model after 8 deaths [130, 131]. Assuming the median OS post-vaccine 4 is 24 months, approximately 24 months after the 16 th patient undergoes migration studies will 8 deaths be observed.

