15.7.1 Exploratory Objective #1: Migration and CCL3

Objective	To assess the relationship between serum CCL3 levels and increased DC migration.
Analysis Set	All patients who undergo migration studies who have CCL3 levels measured.
Outcome	Correlation coefficient between fold change of CCL3 and migration.
Hypothesis	We hypothesize that fold change in CCL3 will be highly correlated with increased migration.

Analysis Plan	A Spearman rank correlation coefficient will assess the association between CCL3 change from pre to post-vaccine 4, and migration.
Additional Analyses	As an additional exploratory analysis of CCL3, a one-sample t-test or a Wilcoxon rank sum test will assess whether fold change in CCL3 between pre- and post-Td pre-conditioning differs from 0.

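### Sections 15.6.3 and 15.7.1 name the Wilcoxon rank sum test, a test for two independent groups, for within-patient fold changes; the signed rank test fits

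*Combined protocol and SAP*

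**What the plan says.** Two places name the test.

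- **Section 15.6.3, Additional Analyses.** On the change from baseline to leukapheresis 2: "the Wilcoxon rank sum test will assess whether significant fold changes occur at pheresis 2". No alternative test is given. Earlier in the same cell, the comparison of leukapheresis 2 with vaccine 6 is to be made "using either a paired t-test or a Wilcoxon signed rank test".
- **Section 15.7.1, Additional Analyses.** On CCL3: "a one-sample t-test or a Wilcoxon rank sum test will assess whether fold change in CCL3 between pre- and post-Td pre-conditioning differs from 0". The scale of the fold change is not defined.

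Section 12.7.5 shows where the paired samples come from. For polyfunctionality: "The immune monitoring blood drawn at pre-vaccine #1 will be the baseline for polyfunctional T cell analysis". For CCL3: "Serum/plasma will be measured to determine levels of CCL3 from the blood drawn at the Td preconditioning visit, and at the vaccine #4 visit". Section 15.1 describes a single-arm study. Table 1 lists the mean fold change in polyfunctionality at leukapheresis 2 under a secondary objective and the mean CCL3 fold change under an exploratory one.

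**The concern.** The rank sum test asks whether two independent samples come from the same distribution. In both places the quantity of interest is a fold change formed from two samples of the same patient. That gives one value per patient, to be compared with a fixed no-change value, and the rank sum test has no form that does this.

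An analyst who follows the text has two options. One is to substitute a suitable test later, perhaps after seeing the data. The other is to drop the fold change and compare the pre and post values as if they came from different people. The second option can be run, but it ignores the pairing and loses power.

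Section 15.7.1 has a further gap. Its null value of 0 is right for a log ratio or a relative change, but for a plain post/pre ratio no change is 1. If only the test name were corrected and the fold change were a plain ratio, the test would reject whatever the data showed.

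**Working it through.** The plan gives no figure for either test, so the check has three parts: the structure of the data, an illustration of the power at stake, and the null value.

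**1. Structure**

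| | 15.6.3 | 15.7.1 |
|---|---|---|
| First sample | pre-vaccine 1 | Td visit, before Td |
| Second sample | leukapheresis 2 | vaccine 4 visit |
| Same patients? | yes | yes |
| Second group? | none | none |
| Test named | rank sum | one-sample t-test or rank sum |
| Test that fits | signed rank | one-sample t-test or signed rank |

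The one-sample t-test in 15.7.1 and the signed rank test elsewhere in 15.6.3 both show that a one-sample or paired analysis was intended.

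**2. Power, if pre and post values were run as independent groups**

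Assumptions (not document figures): normal pairs on the log scale, true shift d = 0.5 SD, within-patient correlation r = 0.5 or 0.8, two-sided 0.05.

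The standardised paired effect is d / √(2(1 − r)):

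- r = 0.5: 0.5 / √1.0 = 0.50
- r = 0.8: 0.5 / √0.4 = 0.79

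The paired test gains from the correlation; the rank sum test does not use it.

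Simulated power, with ranges showing the spread over repeat runs:

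| n | Source of n | r | Rank sum | Signed rank |
|---|---|---|---|---|
| 24 | 15.6.3 | 0.5 | 34% | 62–63% |
| 24 | 15.6.3 | 0.8 | 30–31% | 95% |
| 40 | 15.2 and 15.6.2 | 0.5 | 61–62% | 86–87% |
| 40 | 15.2 and 15.6.2 | 0.8 | 66–68% | over 99% |
| 16 | cap on migration set, 15.2 | 0.5 | 19–20% | 43–44% |
| 16 | cap on migration set, 15.2 | 0.8 | 13–14% | 80–81% |

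With no true shift, the rank sum test rejects in under 1% of runs in every cell, against 4% to 5% for signed rank. The misuse costs power; it does not create false positives.

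Two sizes are shown for 15.7.1 because the documents point both ways. Its analysis set row requires migration data, capped at 16 patients, and the number may be smaller because labelling stopped with v.20220204. Section 15.2, however, includes all patients who reach vaccine 4 in CCL3 analyses, and 15.6.2 anticipates 40. The pre/post CCL3 test needs no migration data.

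**3. Null value in 15.7.1**

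A plain post/pre ratio of positive levels is always positive. If all n values lie above the null value, the exact two-sided signed rank p-value is 2 × 2⁻ⁿ:

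- n = 5: 0.0625
- n = 6: 0.031
- n = 16: 0.00003

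So from 6 patients on, plain ratios tested against 0 are always significant at 0.05, even when CCL3 has not changed.

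**The case against.** The strongest reply is that the intent is plain. Section 15.6.3 uses the correct name for its other paired comparison, and 15.7.1 sets the test beside a one-sample t-test. A competent analyst would run the signed rank test without being told. The power losses above belong to an unpaired analysis that the plan does not describe, and they rest on an assumed shift and assumed correlations. All of that stands. It makes this a low-severity wording error and makes the power figures illustrations only. It does not make the text right: for the leukapheresis 2 change, rank sum is the only test named.

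The null-value point is also conditional. If fold change means a log ratio or a relative change, 0 is correct. The plan does not say which is meant.

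A reader might also infer that the two remaining survival biomarkers have no test level, because their analysis plans mention only intervals, as in "The hazard ratio associate with a 1-unit increase in CCL3 will be estimated with 95% confidence intervals". The documents do not support that. Section 15.6 says that the power calculations for the three predictors "will be adjusted to account for multiple comparisons using a Bonferroni correction, and will use a type I error rate of 0.0167", and the power rows of 15.6.2 and 15.6.3 state a two-tailed 0.0167 for the same Cox models. The deaths quoted there reproduce from (z(1−α/2) + z(0.8))² / (SD² × ln(HR)²):

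- CCL3 (SD 12.9, HR 0.95): 23.9, so 24 deaths
- Polyfunctionality (SD 1.589, HR 0.6): 15.9, so 16 deaths

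Section 15.6.1 records that "the plans for examining the relationship between migration and survival have been dropped", which leaves two tests. Keeping 0.0167 for each bounds the joint error at 2 × 0.0167 = 0.033, below 0.05. That is valid and conservative.

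**Conclusion.** The point holds, at low severity. The Wilcoxon rank sum test is the wrong test as written in 15.6.3 and 15.7.1, because each patient supplies both measurements and there is no second group. This follows from the text alone and needs no assumption. It is probably a naming slip.

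The size of any loss depends on what the analyst does. It is nil if signed rank is run anyway. If pre and post values are treated as independent, the loss is substantial under the assumed 0.5 SD shift and correlations of 0.5 to 0.8. For 15.7.1 it also depends on whether about 40 patients or at most 16 are analysed.

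The null-value problem arises only if fold change is a plain ratio. In that case the result of 15.7.1 would carry no information.

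A reader should not infer that the trial's main conclusions are at risk. The primary endpoint, the sample size, the safety rules and the Cox models for the biomarkers are unaffected.

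**What to change.** - **Sections 15.6.3 and 15.7.1, Additional Analyses:** replace rank sum with signed rank, applied to each patient's paired change.
- **Section 15.7.1:** state that log fold change is tested against 0. On the plain post/pre scale the same no-change value is 1.
- **Optional, editorial only:** in 15.6.2 and 15.6.3, label the 95% confidence intervals as descriptive, since the stated level for the Cox tests is 0.0167.

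The cost is a few words in the SAP, best changed before the biomarker data are examined. No new data, visits or patients are needed.
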